Table 8:	Ectropion Scoring.....	33
Table 9:	Demographic Data Summary Tables and Figures.....	41
Table 10:	Efficacy Data.....	41
Table 11:	Safety Data.....	44
Table 12:	Pharmacokinetic Data.....	47
Table 13:	Planned Listings.....	47
Table 14:	Planned Figures.....	49

List of Figures

Figure 1:	Double-blind Study Design.....	9
Figure 2:	Open-label Study Design.....	10
Figure 3:	Standardized Layout.....	51
Figure 4:	Planned Table Shells.....	53

1. Overview

This statistical analysis plan (SAP) describes the planned analysis and reporting for Mayne Pharma protocol number 18-ICH-001 (A Phase 2 Randomized, Multi-center, Double-blind, Vehicle-controlled, 90-Day, Safety, Efficacy, and Systemic Exposure Study followed by a 90-Day Open-label Extension of Trifarotene (CD5789) Cream HE1 in Adults and Adolescents with Autosomal Recessive Ichthyosis with Lamellar Scale), version 3.0 dated 26-Oct-2020. Reference materials for this statistical plan include the protocol and the accompanying sample data collection documents. Operational aspects related to collection and timing of planned clinical assessments are not repeated in this SAP unless relevant to the planned analysis.

The structure and content of this SAP provides sufficient detail to meet the requirements identified by the Food and Drug Administration (FDA), European Medicines Agency (EMA), and International Conference on Harmonization (ICH) of Technical Requirements for Registration of Pharmaceuticals for Human Use: Guidance on Statistical Principles in Clinical Trials.¹ All work planned and reported for this SAP will follow internationally accepted guidelines, published by the American Statistical Association² and the Royal Statistical Society,³ for statistical practice.

The planned analyses identified in this SAP may be included in clinical study reports (CSRs), regulatory submissions, or future manuscripts. Also, post-hoc exploratory analyses not necessarily identified in this SAP may be performed to further examine study data. Any post-hoc or unplanned, exploratory analysis performed will be clearly identified as such in the final CSR.

Upon sponsor discretion, this study was terminated before the study completed enrollment; however, all planned analyses will still occur. Sixty-five (65) subjects were enrolled in the study before termination. The statistical plan described hereafter is an *a priori* plan. It will be submitted to file prior to any unblinded inferential or descriptive analysis of data pertaining to Mayne Pharma's study 18-ICH-001.

2. Study Objectives and Endpoints

2.1. Study Objectives

2.1.1. Primary Objective

The primary objective is to compare the safety and efficacy of 2 concentrations of trifarotene cream HE1 versus vehicle in adults and adolescents with moderate to severe autosomal recessive ichthyosis with lamellar scale, also known as lamellar ichthyosis (LI) after 90 days of treatment.

2.1.2. Secondary Objectives

The secondary objectives are:

- To assess systemic exposure to trifarotene and its major metabolites after topical application of the investigational product (IP) on up to 90% body surface area (BSA) twice weekly.
- To assess safety for up to 180 days of dosing with open-label trifarotene cream HE1 200 µg/g.

2.2. Study Endpoints

2.2.1. Safety Endpoints

The safety endpoints of this study include the following:

- Reported serious adverse events (SAEs), treatment-emergent AEs (TEAEs), and changes in clinical laboratory tests, vital signs, physical examinations, and 12-lead electrocardiograms (ECGs)
- Local tolerability (Scale: 0-3 [none, mild, moderate, severe], determined by the investigator) for each body area (chest/abdomen, back, legs, arms, and face/neck).

2.2.2. Efficacy Endpoints

2.2.2.1. Primary Efficacy Endpoint

The primary efficacy endpoint of this study is the proportion of subjects in each treatment group who experience successful resolution of LI where “success” is defined as clear/almost clear on treated areas and at least a 2-grade change from Baseline at Day 90/end-of-treatment (EOT) in the Double-blind Period on the 5-point Investigator Global Assessment (IGA) full body scale.

2.2.2.2. Secondary Efficacy Endpoints

The secondary efficacy endpoints of this study include the following:

- The difference in mean scores between the active trifarotene cream HE1 and vehicle groups in the following assessment indices from Baseline through Day 90:
 - 5-point Visual Index for Ichthyosis Severity (VIIS) for scaling (overall 16 points for scaling, i.e., 0-4 points for 4 body areas: chest/abdomen, back, arms, and legs)
 - Individual score for roughness (Scale: 0–4) overall
 - Palm/sole Assessment (Scale: 0–4)
 - Quality of life per Dermatology Life Quality Index (DLQI) and children’s DLQI (cDLQI)
- The difference in proportion of subjects with presence of fissures on palms/soles (presence/absence, number of fissures, and pain associated with fissures on a 0-3 scale) at Day 90 between the active trifarotene cream HE1 and vehicle groups

2.2.2.3. Exploratory Efficacy Endpoints

The exploratory efficacy endpoints of this study include the following:

- The difference in mean ectropion (Ectropion Severity Score [ESS] of 0–8) scores between the active trifarotene cream HE1 and vehicle groups from Baseline through Day 90
- The difference in quality of life per EQ-5D-5L and EQ-5D-Y score between the active trifarotene cream HE1 and vehicle groups from Baseline through Day 90

2.2.3. Pharmacokinetic Variables

The pharmacokinetic (PK) endpoints of the study include plasma concentrations of CD5789 and its major metabolites.

3. Overall Study Design and Plan

3.1. Overall Design

This is a 2-cohort, multicenter study in subjects with moderate to severe LI (i.e., 3–4 on a 5-point Investigator’s Global Assessment [IGA] where 0 = clear; 1 = almost clear; 2 = mild; 3 = moderate; 4 = severe). Adults (Cohort A) and adults and adolescents (Cohort B) will be randomized in a double-blind fashion to 1 of 2 doses of trifarotene cream HE1 or vehicle and treated twice weekly for 90 days.

Approximately 15 adults (≥ 18 years old) will be randomized into the first cohort of subjects (Cohort A) in a 1:1:1 ratio to trifarotene cream HE1 100 $\mu\text{g/g}$, trifarotene cream HE1 200 $\mu\text{g/g}$, or vehicle and treated twice weekly for up to 90 days. After the initial 15 subjects complete at least 28 days of treatment, an independent data safety monitoring board (DSMB) will review aggregate safety and tolerability data.

If no safety issues are identified, both adults and adolescents (ages 12 to 17 years, inclusive) will be allowed to enroll in Cohort B. Subjects in Cohort B will be randomized 1:1:1 to trifarotene cream HE1 100 $\mu\text{g/g}$, trifarotene cream HE1 200 $\mu\text{g/g}$, or vehicle and treated twice weekly for up to 90 days in the same manner as subjects in Cohort A. All subjects (Cohort A and Cohort B) who complete the randomized, Double-blind Period of the study will be eligible to enter a 90-day, Open-label Extension (OLE) in which additional PK, safety, and efficacy data will be collected. Subjects in the OLE will receive open-label trifarotene cream HE1 200 $\mu\text{g/g}$ twice weekly for up to 90 days. A schematic of each period is provided in [Figure 1](#) and [Figure 2](#).

Figure 1: Double-blind Study Design

[figure not shown]
[figure not shown]

Figure 2: Open-label Study Design

The first cohort of 15 adult subjects is a reasonable sample size to assess safety and tolerability before enrolling adolescents. Accounting for a 20% drop-out/nonevaluable rate, a total sample size of 120 subjects randomized in a 1:1:1 ratio to 2 active trifarotene cream HE1 arms and a vehicle cream arm will provide >80% power to detect a difference between each separate trifarotene cream HE1 arm (32 evaluable subjects) and the vehicle cream arm (32 evaluable subjects) 2-sided Fisher's Exact Test assuming a 70% success rate and a 40% success rate, respectively. This study is not powered to detect a difference between the 2 active arms.

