4.1. Introduction

Data processing, tabulation of descriptive statistics, calculation of inferential statistics, and graphical representations will be performed primarily using SAS (release 9.4 or higher). If the use of other software is warranted, the final statistical methodology report will detail what software was used for what purposes.

Continuous (quantitative) variable summaries will include the number of subjects (n) with nonmissing values, mean, standard deviation (SD), standard error (SE), median, minimum, and maximum.

Categorical (qualitative) variable summaries will include the frequency and percentage of subjects who are in the particular category or each possible value. In general, the denominator for the percentage calculation will be based upon the total number of subjects in the study population for the treatment groups, unless otherwise specified. The denominator for by-visit displays will be the number of subjects in the relevant study population with nonmissing data at each study visit.

The minimum and maximum will be reported with the same degree of precision (i.e., the same number of decimal places) as the observed data. Measures of location (mean and median) will be reported to 1 degree of precision more than the observed data and measures of spread (SD, SE) will be reported to 2 degrees of precision more than the observed data.

Percentages will be presented to 1 decimal place, unless otherwise specified and with the following exceptions: a percentage of 0% will not be displayed (i.e., only the count of 0 will be displayed), and a percentage of 100% will be displayed with 0 decimal places.

Unless otherwise indicated, all statistical tests will be conducted at the 0.05 significance level using 2-tailed tests, and *P* values will be reported. Corresponding 95% confidence intervals (CIs) will be presented for statistical tests. A *P* value of ≤ 0.10 but > 0.05 will be considered evidence of a trend.

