4.2. Interim Analysis and Data Monitoring

The DSMB will meet after 15 subjects in Cohort A have completed at least 28 days of double-blind treatment to review aggregate safety and tolerability data (including PK concentration data, PK parameters, and ECG results). The safety data will be unblinded. At that time, the DSMB will decide whether Cohort B (adults and subjects aged 12–17) may begin enrolling, or if additional adult safety data are required before allowing subjects aged 12 – 17 to participate in the study. The DSMB will meet again after 60 subjects have enrolled in the study. The sponsor may request additional reviews, e.g., should any other findings/issues pertaining to safety emerge requiring DSMB review. Details of the DSMB operation will be developed in conjunction with the members of the DSMB before the first meeting and will be modified as required. The unblinded DSMB outputs will not be seen by anyone except the DSMB and the performing statistician.

The primary analysis period is the first 90 days of treatment (i.e., the Double-blind Period). Overall unblinding will take place at the end of the Double-blind Period of the study only after database lock has been achieved. The data will be cleaned and frozen and an unblinded analysis of the data will be performed. The data will be considered final at this point and no changes to these data will be permitted following unblinding with the exception of outcomes and end dates of ongoing AEs and concomitant mediations. A second analysis will take place for endpoints assessed from Day 90 through the OLE.

The protocol assumes a 20% dropout/non-evaluable rate. This rate will be continuously monitored throughout the COVID-19 pandemic. In the event that this rate dramatically increases, a blinded sample size reestimation may be performed to ensure statistical power for the primary endpoint is maintained using the assumptions in Section 3.2.

5. Analysis Populations

The following 5 analysis populations are planned for the Double-blind Period of this study:

- **Safety:** all subjects who are randomized to treatment and receive at least 1 application of study drug in the Double-blind Period. This population will be the primary population for analyses of safety. Subjects will be analyzed by actual treatment received.

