6.1.3. Multiple Comparisons

No adjustments will be made for multiple comparisons. All *P* values for the secondary and exploratory endpoints will be provided in the summary tables for informational purposes only.

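### The claimed power of more than 80% is about 62% at the plan's own 32 evaluable subjects per arm, and roughly 31–45% at the 65 subjects enrolled

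*SAP*

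**What the plan says.** The sample-size paragraph stands at the end of SAP Section 3.1 (Overall Design) in the text at hand. Section 4.2 refers to its assumptions as being in Section 3.2. It plans 120 subjects randomised 1:1:1, allows for 20% dropout or non-evaluability, and states that this "will provide >80% power to detect a difference between each separate trifarotene cream HE1 arm (32 evaluable subjects) and the vehicle cream arm", the vehicle arm also having 32 evaluable subjects. The test and rates are given as a "2-sided Fisher's Exact Test assuming a 70% success rate and a 40% success rate, respectively".

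Two other sections complete the inputs. Section 4.1 sets the level: "all statistical tests will be conducted at the 0.05 significance level using 2-tailed tests". Section 6.1.3 says "No adjustments will be made for multiple comparisons", so each dose is compared with vehicle at the full 0.05.

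Section 1 (Overview) reports that the sponsor stopped the study early and that all planned analyses will still be done: "Sixty-five (65) subjects were enrolled in the study before termination". The power statement was not revised. Section 4.2 still provides that, if dropout rises sharply, "a blinded sample size reestimation may be performed to ensure statistical power for the primary endpoint is maintained".

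**The concern.** The power statement gives the test, both success rates and the evaluable number in each arm, and the level is fixed elsewhere, so it can be checked without outside information. A 30-point difference around a midpoint of 55% is a demanding setting for Fisher's test with 32 per arm, and more than 80% looked too high.

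The claim concerns the primary endpoint, in a document described as an a priori plan to be filed before unblinding. If power is believed to exceed 80%, a non-significant result is likely to be taken as evidence against a 30-point effect. If power is about 62%, the planned design would miss that effect nearly four times in ten. At 65 subjects it would miss it more often than not.

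**Working it through.** **Inputs, all from the SAP.** Active 70%, vehicle 40%, 32 evaluable per arm, two-sided Fisher's exact test, each dose tested separately (Section 3.1); two-sided 0.05 (Section 4.1); no multiplicity adjustment (Section 6.1.3).

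**The dropout arithmetic is right.** 120 / 3 = 40 per arm; 40 × 0.8 = 32.

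**The power does not reproduce.** With X ~ Bin(n₁, 0.70) and Y ~ Bin(n₂, 0.40),

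Power = Σₓ Σᵧ P(X = x) P(Y = y) · 1[Fisher two-sided p(x, y) ≤ 0.05]

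| Evaluable per arm | Fisher power |
|---|---|
| 32 (the plan) | 61.9% |
| 40 (no dropout at all) | 72.5% |
| 47 | 78.6% |
| 48 | 80.05% |

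At 48 evaluable per arm and 20% loss, 48 / 0.8 = 60 per arm must be randomised, or 180 in total against the 120 planned.

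**Would another method give more than 80% at 32 per arm?** The pooled normal approximation is easily checked by hand. The standard error under the null is √(2 × 0.55 × 0.45 / 32) = 0.1244, and under the alternative √((0.21 + 0.24) / 32) = 0.1186. Then

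Φ[(0.30 − 1.96 × 0.1244) / 0.1186] = Φ(0.474) = 68.2%

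Other variants at 32 per arm:

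| Method | Power |
|---|---|
| Normal, continuity-corrected | 58.3% |
| Arcsine | 68.8% |
| Pearson chi-square, uncorrected, exact enumeration | 71.3% |
| Normal, unpooled | 71.6% |
| Fisher, one-sided 0.05 | 71.4% |
| Normal, one-sided 0.05 | 78.9% |

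None reaches 80%. The variants that pass it depart from the stated design. They use 40 per arm with an unpooled normal test (80.7%) or a one-sided normal test (86.5%), or they pool the two doses, 64 against 32, with a normal test (81.2%). Fisher's test on the pooled doses gives 78.9%. Even the chance that at least one of the two doses succeeds, both at 70% and sharing the vehicle arm, is about 77%.

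**How far would the rates have to move?** At 32 per arm, Fisher power passes 80% if vehicle success is 33% or lower (81.7%; at 34% it is 79.3%), or if active success is 77% or higher (82.2%; at 76% it is 79.7%). The SAP assumes neither.

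**At 65 enrolled.** The SAP gives no arm sizes, so a near-equal split is assumed: 65 / 3 ≈ 21.7 per arm, and 21.7 × 0.8 ≈ 17 after 20% loss.

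| Active vs vehicle | Fisher power |
|---|---|
| 17 vs 17 | 31.3% |
| 21 vs 21 | 36.0% |
| 22 vs 22 | 39.7% |
| 21 vs 22 | 43.4% |
| 22 vs 21 | 44.5% |

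**Precision.** The approximate 95% CI half-width for the difference is 1.96 × √(0.45 / n): 23 points at n = 32, 28 at n = 22 and 32 at n = 17.

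**The case against.** Four points can be made for the plan.

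- **The claim is for 120 subjects.** The SAP attaches more than 80% only to that number and openly reports the stop at 65. This stands: the loss of power at 65 follows from a disclosed termination and is not a second miscalculation. It does not touch the error at 32 per arm.
- **The primary analysis is not Fisher's test.** Section 8.1.1 specifies logistic regression with treatment, baseline IGA and age group. Fisher's test is conservative, so the planned model could plausibly have power nearer 70% at 32 per arm, and a miss rate nearer three in ten. This narrows the gap without closing it, and the SAP's own claim names Fisher's test.
- **The 65-subject range is soft.** It rests on an assumed split, and Fisher's discreteness makes it uneven: 17 vs 17 gives 31.3%, but 18 active vs 17 vehicle gives 40.9%. It should be quoted as approximate and with that assumption.
- **Nothing in the analysis changes.** Enrolment is over, Section 8.1.1 already calls for confidence intervals, and the re-estimation clause is conditional and now inert. That is fair, and it makes deleting the clause a matter of tidiness. It is not a reason to file a power figure that is wrong for its own stated inputs.

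**Conclusion.** The concern holds. For the test, rates, level and evaluable numbers printed in the SAP, power is 61.9%, at least 18 points below the stated figure. This part depends on no outside assumption. Two-sided alternatives to Fisher's test at 32 per arm range from about 58% to 72%.

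At the 65 subjects enrolled, Fisher power for the same effect is roughly 31–45%, assuming a near-equal split and between 20% and no loss. That is an unaddressed consequence of stopping early. Because the primary endpoint will be read against this power claim, the statement must be corrected before the plan is filed.

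**What to change.** **Required.** In the sample-size paragraph, replace the claim of more than 80% with about 62% per dose at 32 evaluable per arm (70% vs 40%, two-sided Fisher's exact test, 0.05), and state that it refers to the planned 120 randomised. Add that, with 65 enrolled and a near-equal split, the corresponding power is roughly 31–45% and the expected 95% CI half-width for the difference is about 28–32 percentage points. Note that the sizing test differs from the logistic regression used for the primary analysis.

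**Advisable.** Say that the primary comparison will be interpreted from the estimate and its confidence interval, and that a non-significant result is not evidence of no effect. Remove the re-estimation clause in Section 4.2, which has no function now that enrolment has ended.

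**Cost.** A few sentences of SAP text. No endpoint, model, population or data collection changes; the stated power simply becomes less favourable.

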3.3. Study Population

This study includes adults and adolescents with moderate to severe autosomal recessive ichthyosis with lamellar scale.

3.4. Treatments Administered

For the Double-blind Treatment Period, a fixed dose (determined at Visit 2) of trifarotene cream HE1 100 µg/g or 200 µg/g or vehicle cream will be applied topically twice weekly on up to 90% body surface area (BSA) of each subject. Trifarotene cream HE1 is a cream containing 100 or 200 µg/g (0.01% [w/w] or 0.02% [w/w], respectively) of CD5789. Vehicle contains the same ingredients, without the CD5789. Trifarotene cream HE1 and vehicle will be provided in cream form for topical application and will be packaged in 50-g tubes from which up to 36 g of investigational product (IP) may be dispensed per application, i.e., the maximum dose per

application. Study staff will apply the first dose of study drug to each subject in the clinic on Day 1 after baseline measurements, and will record the amount of study drug applied.

Thereafter, each subject will apply approximately the same amount (up to 36 g) of study drug as for the first dose on up to 90% of BSA twice weekly, sparing the scalp, inguinal, and axillary areas. Subjects will receive an adequate number of tubes to use 1 tube per application and will use a new tube for each treatment day.

For the OLE, all subjects will receive trifarotene cream HE1 200 µg/g and apply the same fixed dose in the same manner as in the Double-blind Period for an additional 90 days.

If the treatment causes application site reactions, the frequency of application will be reduced or interrupted only on the area of concern, as indicated herein. During all clinic visits, the investigator will assess local tolerability (Scale: 0-3 [none, mild, moderate, severe]) for stinging/burning, pruritus, erythema) for each body area (chest/abdomen, back, arms, legs, and face/neck), and the following procedures will be followed:

- If a score of 2 (moderate) is recorded on a local tolerability assessment scale (stinging/burning, pruritus, erythema) on any treated area, the study drug will be applied on that area only once weekly, until the score is back to <2. Continue to treat all other areas twice weekly provided the score is <2 on those areas.
- If a score of 3 (severe) is recorded on a local tolerability assessment scale (stinging/burning, pruritus, erythema) on any treated area, the study drug will not be applied on that area until the score is back to <3 (i.e., “drug holiday”). Continue to treat all other areas twice weekly provided the score is <2 on those areas.

3.5. Method of Assigning Subjects to Treatment Groups

Subjects will be randomized in a 1:1:1 ratio to trifarotene cream HE1 100 µg/g or 200 µg/g or vehicle cream in the Double-blind Period.

Subjects who continue into the OLE will receive trifarotene cream HE1 200 µg/g and apply the same fixed dose in the same manner as in the Double-blind Period for an additional 90 days.

3.6. Blinding and Unblinding

All subjects, investigators, and study personnel involved in the conduct of the Double-blind Period of the study, including data management, will be blinded to treatment assignment with the exception of a specified unblinded statistician and programmer from Premier Research who will have access to the randomization code.

The primary analysis period is the first 90 days of treatment (i.e., the Double-blind Period). Overall unblinding will take place at the end of the Double-blind Period of the study only after database lock has been achieved. A second analysis will take place for endpoints assessed from Day 90 through the OLE.

3.7. Schedule of Events

A detailed schedule of events for the Double-blind period of the study is provided in [Table 1](#). A detailed schedule of events for the OLE is provided in [Table 2](#).

Table 1: Schedule of Events for Double-blind Period

	Screening (-97 days to -1 day) Washout up to 90 Days ^a	Double-blind Treatment Period						
		Baseline (Day 1)	Telephone Visit (Day 7)	Day 14 ± 5 days	Day 30 ± 7 days	Telephone Visit (Day 45)	Day 60 ± 7 days	Day 90 ^{b,c} ± 7 days (ET)
Visit	1	2		3 ^d	4 ^d		5 ^d	6 ^d
Written informed consent/assent	X							X ^a
Assign screening number	X							
Inclusion/exclusion criteria	X	X						
Demographics	X							
Medical history	X							
Physical examination	X	X ^e						X ^e
Vital signs (blood pressure and pulse)	X	X		X	X		X	X
Height, weight, and BMI	X							X ^b
IGA assessment ^f	X	X		X	X		X	X
VIIS ^g assessment	X	X		X	X		X	X
Roughness assessment ^h	X	X		X	X		X	X
Palm/sole assessment	X	X		X	X		X	X
Palm/sole fissuring assessment ⁱ	X	X		X	X		X	X
Ectropion score	X	X		X	X		X	X
Photographs ^j		X			X			X
Quality of life per Dermatology Life Quality Index (DLQI)		X		X	X		X	X
EQ-5D Quality of Life Questionnaire		X		X	X		X	X
12-lead ECG ^k	X	X			X			X

	Screening (-97 days to -1 day) Washout up to 90 Days ^a	Double-blind Treatment Period						
		Baseline (Day 1)	Telephone Visit (Day 7)	Day 14 ± 5 days	Day 30 ± 7 days	Telephone Visit (Day 45)	Day 60 ± 7 days	Day 90 ^{b,c} ± 7 days (ET)
Visit	1	2		3 ^d	4 ^d		5 ^d	6 ^d
Clinical laboratory tests (hematology, chemistry, urinalysis) ^l	X	X			X			X
Serology (hepatitis B surface antigen, hepatitis C)	X							
Coagulation panel		X			X			X
Pregnancy test for female subjects (serum at Screening; urine subsequently) ^m	X	X			X		X	X
Randomization via IWRS		X						
PK blood sample collection ⁿ		X		X	X		X	X
Initial study drug application by clinic staff and measurement ^o		X						
Application instructions, advice on emollient and sunscreen use		X	X	X	X	X	X	X
Dispense study drug and diaries ^p		X		X ^p	X ^p		X ^p	(X) ^p
Concomitant medications	X	X	X	X	X	X	X	X
Tolerability assessment		X		X	X		X	X
Adverse events (and review diaries)		X	X	X	X	X	X	X
Collect all used/unused study drug ^q				X	X		X	X
Provide information about OLE option					X	X	X	X

Abbreviations: BMI = body mass index; DLQI = Dermatology Life Quality Index; ECG = electrocardiogram; ET = early termination; HEENT = head, eyes, ears, nose, throat; ICF = informed consent form; IGA = Investigator’s Global Assessment; IWRS = interactive web response system; OLE = open-label extension; PK = pharmacokinetic; WOCBP = women of childbearing potential; VIIS = Visual Index for Ichthyosis Severity

- a. Upon signing informed consent and entering the Screening Period, subjects will stop using physical and medical treatments for LI, including balneotherapy, and begin to washout prohibited topical and systemic treatments with designated washout periods, as applicable. Before asking a subject to enter washout, investigators should confirm the subject meets study eligibility criteria, except for LI severity (Inclusion Criterion #3). Washout may be up to 90 days. After completing any necessary Washout Period, subjects must return to the site within 35 days before the Baseline Visit within the 97-day Screening Period to have their LI severity assessed and study eligibility requirements determined. During washout, subjects may continue their standard of care of visible skin (face and scalp) for cosmetic reasons and of extremities (palms/soles) to avoid functional consequences on walking or moving their fingers. In the US/EU, this may include compounded emollients with keratolytics (alpha or beta hydroxyl acids) and/or urea. The investigator should approve and document these standard of care treatments in the electronic case report form (eCRF). If the standard of care treatments of the face and/or palms/soles contain prohibited medications, they must be stopped at the Baseline Visit. Subjects may shower, but not bathe or swim, during the Screening Period.
- b. Day 90 procedures should be conducted for subjects who terminate the study early. If a subject discontinues IP, but continues to attend clinic visits, Day 90 will occur as scheduled. Day 90 will be the first visit of the OLE for subjects who choose to continue. Subjects who decide to continue into the OLE will have the following additional procedures: 1) sign informed consent; 2) will be weighed; 3) will be instructed on study drug application; 4) will be given new diaries, and 5) will be provided with study drug.
- c. A Follow-up telephone call will be made within 14 days after Day 90 to subjects who choose not to continue into the OLE to assess any ongoing adverse events.
- d. Although it is preferable to conduct all necessary study assessments in person (onsite visits), this may not be possible as a result of COVID-19-related travel restrictions. To ensure the safety of subjects, investigators, and site staff, Visits 3-6 and unscheduled visits may be conducted remotely. Screening and baseline visits must be performed onsite only, and must be postponed or scheduled for when onsite visits can be safely conducted.
- e. Limited physical examination to include HEENT, cardiorespiratory, abdomen, range of motion.
- f. IGA: 0 = clear; 1 = almost clear; 2 = mild; 3 = moderate; 4 = severe.
- g. VIIS scale for each body area: chest/abdomen, back, legs, and arms, for a possible overall score = 16.
- h. Roughness (0-4 scale);
- i. Palm/sole fissuring assessment: present/absent/number/pain (0-3 scale).
- j. Photography will be performed at sites with the capability for subjects who sign a photographic ICF. A central reader who will not be an investigator in the study will review the photographs to assess consistency of investigator scoring of LI severity as a quality check.
- k. ECG to be conducted at Screening, Baseline, Day 30, and Day 90 for all subjects. Subjects in the PK substudy will also have postdose ECGs at each serial blood draw on Day 1 and Day 30.
- l. Subjects must be fasting (i.e., at least 8 hours) for clinical laboratory tests, but not for PK blood draws.
- m. Note: Subjects who are premenstrual at Screening but begin menses during the course of the study should follow the pregnancy testing schedule for WOCBP correlating to the visit menses began.
- n. Samples for PK will be drawn from all subjects at Baseline and at each clinic visit. At selected sites among subjects who consent to participate in the PK substudy, samples will be taken predose and at 1, 2, 4, 8, 12, and 24 hours postdose on Day 1. On Day 30, IP will be applied in the clinic for PK substudy subjects, and PK samples will be taken predose and at 1, 2, 4, 8, 12, and 24 hours postdose. Trough levels will be drawn when the subjects are in the clinic for other study visits (i.e., Day 14, Day 60, and Day 90). Visits for PK must occur at least 24 hours after the last application of the IP to avoid contamination of the blood samples with any IP that may have remained in the skin after the last application.
- o. Study staff will apply initial dose of study drug in the clinic after Baseline measurements, and the amount of study drug used will be measured (i.e., 36-g tube will be measured before and after application to determine amount used).
- p. Study drug provided in 50-g tubes (maximum single application is 36 g). Measure study drug kits (tubes and box, but not leaflets) before dispensing; subjects must record days/times of study drug application in the diaries and any areas of skin not treated, e.g., due to local reactions. Dispense enough additional study drug until next visit (except at Day 90, unless subject consents to continue into OLE).

- q. Confirm study drug compliance by weighing the studykits (tubes and boxes, but not leaflets) and reviewing diary.

Table 2: Schedule of Events for Open-label Extension

	Open-label Treatment Period ^a						Follow-up
	Telephone Visit (Day 97) ^a	Day 104 ± 5 days	Day 120 ± 7 days	Telephone Visit (Day 134)	Day 150 ± 7 days	Day 180 ± 7 days/ET	Day 194 or 14 days after End of Open-label Treatment
Visit		7 ^a	8 ^a		9 ^a	10 ^a	11 ^a
Informed consent ^b							
Physical examination ^c						X	X
Vital signs (blood pressure and pulse)			X	X	X	X	X
Record IGA ^d		X	X		X	X	X
VIIS ^e assessment		X	X		X	X	X
Roughness assessment ^f		X	X		X	X	X
Palm/sole assessment		X	X		X	X	X
Palm/sole fissuring assessment		X	X		X	X	X
Ectropion score		X	X		X	X	X
Clinical laboratory tests (hematology, chemistry, urinalysis) ^g			X			X	
Pregnancy test for female subjects (urine) ^h			X		X	X	X
Coagulation panel			X			X	
12-lead ECG			X			X	
PK blood sample collection ⁱ			X			X	
Application instructions, advice on emollient and sunscreen use ^j	X	X	X	X			
Dispense study drug and diaries ^k		X	X		X		
Concomitant medications	X	X	X	X	X	X	X

	Open-label Treatment Period ^a						Follow-up
	Telephone Visit (Day 97) ^a	Day 104 ± 5 days	Day 120 ± 7 days	Telephone Visit (Day 134)	Day 150 ± 7 days	Day 180 ± 7 days/ET	Day 194 or 14 days after End of Open-label Treatment
Visit		7^a	8^a		9^a	10^a	11^a
Tolerability assessment		X	X		X	X	
Adverse events (and review diaries)	X	X	X	X	X	X	X
Collect all used/unused study drug ¹		X	X		X	X	

Abbreviations: ECG = electrocardiogram; ET = early termination; HEENT = head, eyes, ears, nose, throat; ICF = informed consent form; IGA = Investigator's Global Assessment; PK = pharmacokinetic; OLE = open-label extension; VIIS = Visual Index for Ichthyosis Severity; WOCBP = women of childbearing potential

- Although it is preferable to conduct all necessary study assessments in person (on -site visits), this may not be possible as a result of COVID-19-related travel restrictions. To ensure the safety of subjects, investigators, and site staff, Visits 7-11 and unscheduled visits may be conducted remotely.
- Subjects will sign the OLE ICF at the Double-blind Day 90 Visit. All efficacy assessments, safety/tolerability assessments, including clinical laboratory testing and PK from Day 90 will be carried over for the OLE and will not be repeated.
- Limited physical examination to include HEENT, cardiorespiratory, abdomen, range of motion.
- IGA: 0 = clear; 1 = almost clear; 2 = mild; 3 = moderate; 4 = severe
- VIIS scale for each body area: chest/abdomen, back, legs, and arms, for a possible overall score = 16.
- Roughness (0-4 scale); fissuring assessment on palms/soles: present/absent/number/pain (0-3 scale).
- Subjects must be fasting (at least 8 hours) for clinical chemistry testing, but not for PK only blood draws.
- Subjects who are premenstrual at Screening but begin menses during the course of the study should follow the pregnancy testing schedule for WOCBP correlating to the visit menses began.
- Samples for PK will be drawn from all subjects at Day 120 and Day 180. Visits for PK must occur at least 24 hours after the last application of the IP to avoid contamination of the blood samples with any IP that may have remained in the skin after the last application.
- Subjects must record days/times of study drug application in the diaries and any areas of skin not treated (e.g., due to local reactions).
- All subjects in the OLE will receive trifarotene 200 µg/g. Study drug provided in 50-g tubes (maximum single application is 36 g). Measure study drug tubes before dispensing. Dispense enough additional study drug until the next visit (except at Day 180).
- Confirm study drug compliance by weighing the study kits (tubes and boxes, but not leaflets) dispensed and returned and reviewing diary.

4. Statistical Analysis and Reporting

